The TJDBPS01 trial is designed as a multicentre, randomized, controlled, superiority trial with two parallel groups in fourteen pancreatic centres among 11 provinces in China, providing a minimum of >50 PDs annually. **(Supplementary file 1)** All the participating fourteen centres with pancreatic surgery expertise have performed ≥ 104 TLPDs and OPDs, respectively.¹⁵ Screening and identification of eligible patients will take place within the participating centres' pancreatic multidisciplinary team (MDT). All patients about to undergo PD will go through a standard evaluation: Contrast-enhanced multi-thin-slice CT scans (1 mm) with or without endoluminal ultrasound (EUS), which will be discussed by the MDT. Magnetic resonance imaging with diffusion-weighted imaging is applied to rule out the suspected metastasis before surgery. Patients recommended for resection on the basis of a high likelihood of a malignant lesion will be contacted and provided with a detailed consensus. Consent (version date 2018-03-20, Ver 1.0) will be obtained by an investigator who should comply with applicable regulatory requirements and adhere to the ethical principles in the Declaration of Helsinki. It is not necessary for patients to have a histological diagnosis of malignancy before surgery provided that the MDT has confirmed that the lesion is concerning enough to require resection.¹⁶ Randomization will be performed in a 1:1 allocation. The patients will be randomized into two groups: (1) patients who will undergo TLPD and (2) patients who will undergo OPD. This study is structured after the SPIRIT 2013 guideline defining standard protocol items for clinical trials. **(Figure 1)**

Study population

All adult patients with an indication for PD, including but not limited to pancreatic cancer, bile duct cancer, duodenal cancer and benign diseases such as mass-forming pancreatitis, will be evaluated and informed of the possibility to take part in the TJDBPS01 trial. After the consent form is signed, participants will be randomized into the two previously mentioned groups.

Patients and public involvement

Neither patients nor the public are involved in the conception, design or conduct of the study.

Participants eligibility

Inclusion criteria

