anastomosis. However, the mattress sutures do not completely penetrate the pancreatic parenchyma but only enter the tissue half-way. The fifth and sixth mattress sutures are supposed to interlock in the anterior wall of the jejunal hole. The fourth layer of the anastomosis has been made between the anterior wall of the pancreatic stump and the anterior wall of the jejunum. Four incompletely transpancreatic interrupting 4-0 prolene mattress sutures are placed to close the gaps in the superoinferior margin of the anastomosis and strengthen the sutures on its anterior wall, achieving a pancreas-enteric anastomosis. Approximately 10 cm distally, an end-to-side hepaticojjunostomy is performed with running (bile duct dilatation of >5 mm) or interrupted (bile duct dilatation of ≤ 5 mm) sutures (Novosyn, BRAUN). Approximately 40 cm distal to the biliary anastomosis, an antecolic side-to-side gastroenterostomy is performed with the staple technique, and 2 layers of running 3-0 sutures (Novosyn, BRAUN) are used to close the gastric stump. Two 27 Fr surgical drains are placed through Winslow and the upper region in the PJ stoma. After haemostatic control, the trocars are removed. The specimen is extracted through an upper-middle incision, which is subsequently closed in layers together with the closure of the trocars. A video clip for illustrative purpose of the basic laparoscopic surgical procedure is available as **Supplementary file 2** and **Supplementary file 3**.

OPD techniques

The open pancreaticoduodenectomy will be performed by the same group of surgeons. A right sided rectus muscle abdominal incision is preferred for better exposure. The key steps are similar to those taken in the TLPD group. Since outcomes of open pancreatectoduodenectomy worldwide are promising and convincing, the surgical technique in the OPD arm reflects their usual practice; also,

the anastomoses will be performed according to each centre's protocol. Procedure variations according to the surgeon's preferences are allowed but must be recorded on the case record form. Two surgical drains are placed as in the TLPD procedure.

Conversion from TLPD to OPD

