predictors of missing values will be identified. The primary outcome analysis will be conducted according to the Intention to treat analysis and will be adjusted for the predictors of missing values as the sensitivity analysis. In addition, multiple imputations will be used to impute missing data, and the imputed data will also be analysed as part of the sensitivity analyses.

Participant timeline

The trial time schedule of enrolment is estimated to be a 2-year period, followed by a 2-year follow-up visit after discharge from the hospital. Once the eligibility of the patients is confirmed, randomization will be applied. When to apply the interventions is not strictly defined: every collaborating centre can make its own preferred adjustment, but this will usually be within 48 hours after the randomization. The assessments and visits for patients are mandatory in the first month, at 3 months, 6 months, 12 months and 24 months, with either telephone or in-hospital follow-up.

(Figure 3)

Sample size

Considering the primary outcome variable is the LOS and according to the latest systemic review,²⁰ MIPD was associated with a shorter length of stay than OPD was (mean difference [MD] -2.95 days, 95% confidence interval [CI] -3.91 to -2.00 days). Accordingly, the sample size is determined based on the primary objective of comparing the LOS between two surgical methods. Based on a mean difference of 2.95 days in the two surgical groups, using the two-sided test with 80% power at a significance level of 5%, the minimal sample size needed to detect a significant difference is calculated to be 274 patients in the TLPD group and 274 in the OPD group ($\alpha=0.05$,

$\beta=0.2$, power=0.8). Considering washout or loss of follow-up, we enlarged the sample size by 20% to compensate for withdrawal/dropout. Then, the final sample size is 656. Thus, there are 328 patients in each group.

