The null hypothesis (H0) is that the mean LOS of TLPD group is the same in OPD group. In another word H0: Mean LOSTLPD = Mean LOSOPD. The alternative hypothesis (HA) is that the mean LOS of TLPD group is not the same in OPD group. HA: Mean LOSTLPD \neq Mean LOSOPD. Two sample t-test are used then if the test statistic turns out that $p>0.05$, then it fails to reject the null. The mean LOS of TLPD group is the same in OPD group. Otherwise, if $p<0.05$, the null hypothesis is rejected. The mean LOS of TLPD group is not the same in OPD group. Base on the previous study and the hypothesis, a -2.95 days of mean differences should be obtained.

Recruitment

Each centre will screen eligible patients through the outpatient department or through advertising by the qualified surgeons. The duration of the recruitment period is estimated to be a 24-month interval depending on each centre's recruiting rate. No financial incentives will be provided to trial investigators or patients for enrolment in the recruitment period.

Participating surgeons and centre criteria

To prevent surgeon bias, participating surgeons must satisfy the following criteria: (1) they must have experience in performing more than 104 TLPDs, (2) they must have experience in performing more than 104 OPDs, and (3) they must have completed the Tongji Hospital TLPD training programme.

All the participating centres represent the largest pancreatic surgery centres in their region, ensuring that 50 PDs are performed annually. If willing to join the trial, each surgeon will be mandated to offer two recently unedited surgery videos for evaluation. The video should be sent to the Board and saved appropriately. Only when the Board approves the surgical techniques can the surgeon and his or her centre participate as a collaborator.

Randomization and allocation

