We applied the stratified randomized block design for the fourteen centres with a block number of 4, and the design is conceived using SAS statistical software (V. 9.3; SAS Institute, USA). The randomization is centralized through a computer-generated system and performed in a parallel fashion. A data manager who is independent of the data analysis or patient enrolment generated the randomization schedule. Allocation will be announced and handled out by the study coordinators only after a baseline assessment and the patient consenting to participate in the study. The randomization schedule will not be available to study recruiters or physicians. Allocation will be conducted by the independent data manager. Specifically, when appropriate patients are enrolled, the researcher will inform the data manager, and then the random number and exact treatment group will be returned simultaneously.

Blinding

The patients and surgeons are unblinded while the data collectors, outcome assessors, and data analysts are blinded. The primary endpoint of this study is the LOS and is not influenceable by the data collectors, outcome assessors, and data analysts. Since they are blinded and also are not

involved in the pre-, peri- and post-operative management of the patients, thus they have no determination of the LOS. The surgeons only perform the surgery and didn't involve in the postoperative management. The patients have little influence concerning the LOS, since once the discharge criteria are reached, they will be discharge immediately. Most of the criteria are objective conditions like do not need any intravenous infusion, incision fully recovered without infection, major organ functioning well and nearly normal haematological parameters. These conditions won't influenced by the patients even they are unblinded.

Data collection

Patient demographics: year of birth, sex, body mass index, surgical risk (ASA score), comorbidities, previous surgical history, main complaint, preoperative biliary drainage, preoperative blood samples (haemoglobin level, white blood cell count, and granulocyte: lymphocyte (G:L) ratio), plasma level of total bilirubin, carbohydrate antigen (CA) 19-9, CA 125, carcinoembryonic antigen (CEA), alpha-fetoprotein (AFP), date of admission, and income.

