Photographers should work in accordance with the visit process requirements, and completed eCRF will be used to enter the original data into the system with a guide; the system cannot automatically identify the data needed to be entered through manual input by the data entry person.

General statistical methods

SAS statistical software (V. 9.4; SAS Institute, USA), the R program (R Foundation for Statistical Computing, Vienna, Austria, version 3.4.4), Power Analysis and Sample Size (PASS, V11.0 NCSS) and other required statistical software programs will be used, when appropriate. All statistical tests will be tested with two sides, and $P < 0.05$ is considered to represent a statistically significant difference, with a confidence interval of 95%. Quantitative data statistics will be described by the number of cases, means, standard deviation (SD), median, quartile (IQR), maximum and minimum (Min ~ Max) values. Qualitative data statistics will be described by the frequency, constituent ratio, or percentage. The effect research and the analysis comparison will select the data set according to the specific research goal with the appropriate statistical analysis method. The inter-group comparison of qualitative data will use the Chi-square test, and the independent sample T test will be used to compare the quantitative data between the groups.

The inter-group comparison of control covariance can be compared by covariance analysis or the generalized linear model.

We used the SPIRIT checklist when writing this study protocol.^{24,25}

Data monitoring

Efficacy and safety of the duration of data acquisition is 90 days after the patient signs the informed

consent (ICF) and the visit. Security data will evaluate the severity of adverse events based on the CTCAE 4.0 standard. All adverse events will be recorded on the CRF, from the signing of the ICF to the end of the study. LinkDoc acts as the independent third party and will conduct data monitoring throughout the whole trial.

Harms

All the harms, including adverse events or even severe adverse events, will be recorded in detail according to the Common Terminology Criteria for Adverse Events (CTCAE ver 4.0). The data will also be collected by the Hospital's Ethical Committee and in the Chinese Clinical Trial Registry.

Protocol amendments

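### The primary t-test on length of stay ignores the centre stratification, so it is conservative and less precise if centre explains part of the variance

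*Protocol*

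**What the plan says.** The Sample size section of the Protocol states the null and alternative hypotheses for mean LOS and then the decision rule: "Two sample t-test are used then if the test statistic turns out that" p exceeds 0.05, the null is retained; otherwise it is rejected. General statistical methods repeats the choice: "the independent sample T test will be used to compare the quantitative data between the groups".

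Randomization and allocation describes a design that the test does not reflect: "We applied the stratified randomized block design for the fourteen centres with a block number of 4". The Design section gives the ratio: "Randomization will be performed in a 1:1 allocation".

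Two passages mention adjustment. Under Missing data, the primary outcome analysis "will be adjusted for the predictors of missing values as the sensitivity analysis". Under General statistical methods, "The inter-group comparison of control covariance can be compared by covariance analysis or the generalized linear model". The first concerns predictors of missingness only, and only as a sensitivity analysis. The second is optional and names neither LOS nor centre. Nothing in the Protocol puts centre into the primary comparison.

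**The concern.** With 1:1 blocks inside each centre, the two arms have nearly the same mix of centres. A level difference between centres that affects both arms alike therefore cancels from the treatment difference. The pooled two-sample t-test does not use this. It counts the spread between centres as random error, so its standard error is larger than the design warrants. If centre matters for LOS, the 95% confidence interval is too wide, the real type I error falls below 5%, and some of the precision that the stratification could give is lost.

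The Protocol gives no between-centre variance, and its text points both ways. In the open arm, "the surgical technique in the OPD arm reflects their usual practice", and anastomoses follow each centre's own protocol. This suggests that centres differ. Against that, Postoperative management sets common discharge criteria, and the Blinding section says of patients "since once the discharge criteria are reached, they will be discharge immediately", which should narrow differences in LOS.

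**Working it through.** **Inputs from the Protocol (Sample size):** difference 2.95 days, two-sided 5% level, 80% power, 274 per arm, raised by 20% to 328 per arm (274 × 1.2 = 328.8).

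**Inputs not in the Protocol:**
- The SD of LOS. It is not stated, so 274 cannot be reproduced independently. Solving for the SD that gives 80% power at 274 per arm yields 12.30 days (non-central t) or 12.32 days (normal approximation). Power of about 80% at 274 is therefore true by construction.
- The share r of LOS variance due to centre. It is assumed at 1%, 5%, 10% and 20%, with centre effects shared by both arms.

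**Formulas, n per arm:**
- Standard error used by the t-test: SE_t = SD × √(2/n).
- True standard error under blocking: SE_b = SE_t × √(1 − r).
- Overstatement: 1/√(1 − r), which does not depend on the SD.
- Real type I error: 2 × [1 − Φ(1.96/√(1 − r))].
- Power of the t-test: 1 − Φ((t_crit × SE_t − 2.95)/SE_b).
- Power with centre in the model: non-central t with SD × √(1 − r) and 2n − 15 degrees of freedom.
- Extra patients per arm for the t-test to match, at 274: 274 × [1/(1 − r) − 1].

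**Worked case, n = 328, r = 10%:** SE_t = 12.30 × √(2/328) = 0.961 and SE_b = 0.961 × √0.9 = 0.911. With t_crit × SE_t = 1.886, unadjusted power is 1 − Φ((1.886 − 2.95)/0.911) = 87.8%. The centre-adjusted model gives 89.8%.

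| Centre share r (assumed) | 1% | 5% | 10% | 20% |
|---|---|---|---|---|
| SE overstated by | 0.5% | 2.6% | 5.4% | 11.8% |
| Real type I error of the t-test | 4.9% | 4.4% | 3.9% | 2.8% |
| Power at 274 per arm, t-test | 80.1% | 80.6% | 81.3% | 82.7% |
| Power at 274 per arm, centre in model | 80.4% | 82.0% | 84.0% | 87.9% |
| Power at 328 per arm, t-test | 86.7% | 87.2% | 87.8% | 89.2% |
| Power at 328 per arm, centre in model | 86.9% | 88.2% | 89.8% | 92.9% |
| 95% CI half-width at 328, t-test (days) | 1.89 | 1.89 | 1.89 | 1.89 |
| 95% CI half-width at 328, centre in model (days) | 1.88 | 1.84 | 1.79 | 1.69 |
| Extra patients per arm to match, at 274 | 3 | 14 | 30 | 69 |

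**Sensitivity to the SD, 274 per arm.** At an assumed 10 days both analyses exceed 93% power. At an assumed 14 days power is 69% to 71% for the t-test and 70% to 79% with centre.

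**Simulation.**
- Fourteen equal centres of 40 (280 per arm), blocks of 4, r = 20%, normal LOS: type I error 3.2% unadjusted and 5.4% adjusted; power 84.1% and 88.9%.
- The same with right-skewed (exponential) LOS: type I error 2.7% and 4.8%; power 83.9% and 88.5%.
- Unequal centres, 656 patients, r = 0, 5%, 10% and 20%: type I error of the t-test 4.7%, 4.5%, 3.9% and 3.8% with normal errors, and 5.2%, 4.6%, 4.4% and 3.4% with lognormal errors. The adjusted model ran from 4.7% to 5.7%; with 6,000 runs the simulation standard error is about 0.3 points. Mean half-width at r = 20% was 1.87 days unadjusted and 1.69 adjusted.

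The direction agrees throughout. The effect on type I error at r = 20% is somewhat smaller with unequal centres than the formula gives.

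**The case against.** The case against has four parts.

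1. The t-test is valid. Type I error stays at or below 5%, planned power is met on the implied SD, and the test matches the two-mean comparison behind the sample size. All of this stands, and it limits the point to efficiency.

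2. The size depends on r and the SD, neither of which is stated. At 328 per arm the gain is 0.2, 1.0, 2.0 and 3.7 percentage points of power across the assumed range, so only the upper part matters much. This stands too. The overstatement of the standard error and the type I error, however, do not depend on the SD.

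3. Common discharge criteria and shared surgeon qualification suggest small centre effects, and usual practice in the open arm is variation in one arm only. A centre main effect removes only what both arms share, so the gains above would be smaller for arm-specific variation. One simulation with centre effects in the open arm only (r = 5%), and centres treated as a random sample, gave type I error of about 10% for both analyses. That result concerns inference to a wider population of centres. With the fourteen centres held fixed, the t-test stayed conservative in simulation, at about 3.0% for shared effects and 3.6% for open-arm-only effects.

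4. Model terms are often left to an SAP, which is not shown here. The Protocol, however, does not leave the test open: it names the t-test as the decision rule. The optional wording on covariance analysis commits to nothing for LOS.

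**Conclusion.** The concern holds as a conditional loss of efficiency. The Protocol fixes an unadjusted test for a trial randomised within centres. If centre explains part of LOS variance, that test is conservative and its interval is wider than the design warrants.

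For assumed centre shares of 5% to 20%, the interval is 2.6% to 11.8% wider than it need be. On an SD of 12.3 days the loss at 328 per arm is about 1 to 4 percentage points of power. At a 1% share it is negligible, and at zero the two analyses practically coincide. These sizes assume that centre effects are shared by both arms and that inference is to the fourteen participating centres. The result of the t-test would not be invalid, but the choice should be changed because the better analysis costs almost nothing.

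**What to change.** In the Sample size section, replace the two-sample t-test as the primary decision rule with a linear model of LOS on treatment, with centre (the randomisation stratum) as a fixed effect. Report the adjusted mean difference with its 95% confidence interval and base the primary conclusion on it. Keep the two-sample t-test as a sensitivity analysis. In General statistical methods, state that the t-test rule for quantitative data does not govern the primary outcome, so that adjustment is not left to a later choice.

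The cost is wording and 13 of 546 degrees of freedom at 274 per arm. It needs no new data and no change to the sample size.

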Total laparoscopic pancreaticoduodenectomy versus open pancreaticoduodenectomy (TJDBPS01): study protocol for a multicentre, randomized controlled clinical trial.

ABSTRACT

Introduction Pancreatoduodenectomy (PD) is one of the most complex abdominal operations to perform, and it is usually conducted for tumours of the periampullary region and chronic pancreatitis. Minimally invasive surgery has been progressively being developed for pancreatic surgery, first with the advent of hybrid-laparoscopy and recently with total laparoscopic surgery. Issues including the safety and efficacy of total laparoscopic pancreaticoduodenectomy (TLPD) and open pancreaticoduodenectomy (OPD) are currently being debated. Studies comparing these two surgical techniques are emerging, and large randomized controlled trials (RCTs) are lacking but are clearly required.

Methods and analysis TJDBPS01 is a multicentre, prospective, randomized controlled, parallel-group, superiority trial in fourteen centres with pancreatic surgery experts who have performed ≥ 104 TLPDs and OPDs. A total of 656 patients who will undergo PD are randomly allocated to the TLPD group or OPD group in a 1:1 ratio. The trial hypothesis is that TLPD has superior or equivalent safety and advantages in postoperative recovery compared with OPD. The primary outcome is the postoperative length of stay (LOS).

Ethics and dissemination The Institutional Review Board Approval of Tongji Hospital, Tongji Medical College, Huazhong University of Science and Technology has approved this trial and will be routinely monitoring the trial at frequent intervals, as will an independent third-party organization. Any results from this trial (publications, conference presentations) will be published in peer-

reviewed journals and conference proceedings.

Trial registration number NCT03138213 in clinicaltrials.gov.

Keywords pancreaticoduodenectomy, laparoscopic surgery, open surgery, whipple, randomized controlled trial.

Article Summary

Strengths and limitations of this study

- The study is designed as a prospective, randomized-controlled trial to achieve conclusion on the highest evidence level to provide the evidence concerning the possible benefits of total laparoscopic pancreaticoduodenectomy (TLPD) over open pancreaticoduodenectomy (OPD) in China, it is (i) multicentric and (ii) internationally registered.

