Similarly, all of the studies that reported results on this topic emphasized the need for large randomized controlled trials (RCT). However, RCTs are difficult to perform and are costly. There should be further consideration regarding the need for detection of numerous surgical, clinical and

oncological variables. Thus, it is imperative for such a study to have enough patients enrolled. A study recruiting an adequate number of patients is desirable. In year 2017, Palanivelu et al published the first RCT worldwide and concluded that LPD offered a shorter hospital stay compared with OPD.¹¹ Poves reached the same conclusion the following year.¹² Both of their studies were conducted in a single-centre setting and recruited only 60 and 66 patients, respectively. The researchers claimed that a multicentre trial will be necessary. LEOPARD-2, the first multicentre RCT, recruited 99 patients but did not reveal the superiority of the TLPD and ended with an estimated mortality rate of 6%; 5 patients died in the laparoscopic group, and 1 patient died in the open group.¹³ This result limited the application of TLPD and hindered the development of the technique throughout the Netherlands. Therefore, a multicentre-based RCT with available expertise in laparoscopy guaranteeing sufficient enrolment is necessary.

Therefore, in this trial, TJDBPS01, a large registry will be created by collecting data from the fourteen qualified centres in China to create a working basis for analysing outcomes of interest and obtaining evidence for comparing TLPD and OPD. Additionally, it will be possible for TJDBPS01 to acquire long-term outcomes of PD patients who have not been reported in any RCT studies.

Objectives

The broad goal of this trial is to evaluate the safety and efficacy of TLPD and OPD procedures. The main hypothesis is that TLPD has superiority advantages in postoperative recovery and is equivalent in safety to OPD. The primary outcome variable is the postoperative length of stay. The secondary outcome variables include estimated blood loss, operation time, complication rate, R0 resection rate, comprehensive complication index (CCI) and overall survival.¹⁴

METHODS AND ANALYSIS

Design

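### The protocol concludes from p>0.05 in the primary t-test that mean length of stay is the same in both arms, which a difference test cannot show

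*Protocol*

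**What the plan says.** The trial is "designed as a multicentre, randomized, controlled, superiority trial with two parallel groups" (Protocol, Design). The primary outcome is postoperative LOS, and "the sample size is determined based on the primary objective of comparing the LOS between two surgical methods" (Sample size).

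The closing paragraph of Sample size sets the null hypothesis of equal mean LOS against a two-sided alternative, names the two-sample t-test, and gives a conclusion for each result:

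- For p>0.05: "then it fails to reject the null. The mean LOS of TLPD group is the same in OPD group".
- For p<0.05: "the null hypothesis is rejected. The mean LOS of TLPD group is not the same in OPD group".

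General statistical methods makes all tests two-sided and takes P<0.05 to "represent a statistically significant difference, with a confidence interval of 95"%. No margin and no equivalence test for LOS appears in the document.

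**The concern.** A p-value above 0.05 means that the data are compatible with no difference. They may be just as compatible with the difference that the trial was built to find. Moving from not rejected to equal treats lack of evidence as evidence of sameness. A claim of sameness needs a margin fixed in advance and a confidence interval lying inside it, and this superiority design has neither for LOS.

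The sentence governs the primary outcome. If followed as written, an inconclusive result becomes a prespecified conclusion that the two operations give the same mean stay, even when the interval still contains the full planned benefit.

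**Working it through.** **1. Is the sentence a conclusion or a restatement of the null?** The null has already been given at the head of the paragraph, once in words and once in symbols. The sentence then follows a test result, and it is matched by a sentence of the same form after p<0.05, which can only be a conclusion. The natural reading is that both are conclusions.

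**2. Inputs (Protocol, Sample size).** Difference 2.95 days; cited 95% CI -3.91 to -2.00 days; two-sided alpha 0.05; beta 0.2; 274 per group before the dropout allowance, 328 per group after it. The SD is not stated.

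**3. The plan's own figure.** Without an SD, 274 cannot be reproduced from the document's inputs. The SD it implies is

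SD = 2.95 × √(274/2) / (1.960 + 0.842) = 2.95 × 11.705 / 2.802 ≈ 12.3 days.

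Putting 12.32 back returns 274 per group, which is circular and confirms only the back-calculation. The 12.3 days is therefore an assumption.

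**4. How often a real benefit would be called sameness.** At a true difference of 2.95 days and 274 per group, P(p>0.05) = beta = 0.20 by design. This is the plan's own figure and needs no added input. It does carry the plan's unstated SD: if the true SD were 10 or 15 days, the figure would be 7% or 37%. With the implied SD, a true benefit of 2.00 days (the weaker limit of the cited interval) gives p>0.05 in 52% of trials.

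**5. What a borderline non-significant result leaves open (274 per group, SD 12.3).**

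- SE = 12.3 × √(2/274) = 12.3 × 0.0854 ≈ 1.05 days.
- 95% CI half-width = 1.96 × 1.05 ≈ 2.06 days.
- At p just above 0.05 the estimate is about -2.06, so the interval runs from about -4.1 to 0 days and contains -2.95.

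**6. Sensitivity to the SD.** The borderline interval contains -2.95 when 2 × t × SD × √(2/274) exceeds 2.95. With t = 1.964 this means SD > 2.95 / (2 × 1.964 × 0.0854) ≈ 8.8 days.

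| SD (days, assumed) | Lower limit at p = 0.05, 274 per group | Contains -2.95? |
|---|---|---|
| 8 | -2.7 | no |
| 10 | -3.4 | yes |
| 12.3 | -4.1 | yes |
| 15 | -5.0 | yes |

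**7. At full recruitment without loss (328 per group, SD 12.3).** The borderline interval is about -3.8 to 0 days. The chance of p>0.05 is 13% at a true 2.95 days and 45% at 2.00 days.

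**The case against.** The strongest defence is that this is loose English beside a correct rule. The test is first said, rightly, to fail to reject, and the next sentence nearly repeats the wording of the null, so it may only name the hypothesis left standing. The section concerns sample size and does not prescribe how results are reported, and the planned 95% confidence intervals would show the imprecision. The error rates above are ordinary type II error and would be the same if the sentence were deleted.

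Part of this stands. No computation depends on the sentence, and the percentages measure how often it would mislead, not a defect in the test. The SD-based figures are illustrations only. But the matched p<0.05 sentence makes the restatement reading the weaker one, and a confidence interval printed beside a conclusion of equality does not withdraw that conclusion.

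A reader might go further and infer that safety will be judged in the same way. Objectives states that "The main hypothesis is that TLPD has superiority advantages in postoperative recovery and is equivalent in safety to OPD", and the Introduction cites a multicentre trial that "ended with an estimated mortality rate of 6%; 5 patients died in the laparoscopic group, and 1 patient died in the open group". The document does not support that inference. The formal hypotheses concern LOS only, no passage says that a non-significant safety result will be read as equivalence, and a safety margin may be set in a statistical analysis plan that is not shown. The missing margin for safety is therefore not part of this point.

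**Conclusion.** The point holds for the primary outcome only. The conclusion attached to p>0.05 is wrong as written and contradicts the correct phrase just before it. The stated beta of 0.2 is enough to show that this matters: one trial in five would declare equal mean LOS even if the full planned benefit were real.

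The interval of about -4.1 to 0 days rests on the back-calculated SD of about 12.3 days and on 274 analysed patients per group. Its message holds for any SD above about 8.8 days and fails at SD 8. The logical error does not depend on the SD. The sentence should be corrected, but it does not undermine the design, the test or the sample size.

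**What to change.** In the closing paragraph of Sample size, replace the sentence that follows the p>0.05 result with: *no difference in mean LOS has been shown; the estimated mean difference and its 95% CI are reported*.

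The cost is one sentence. The hypotheses, t-test, alpha, sample size and data collection do not change.
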